7.1 Clinical observation endpoints

7.1.1 Primary efficacy endpoint

Improvement in self-care ability (proportion of patients with mRS score ≤1) after 90 days of treatment

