12.2 Statistical analysis method

- All statistical tests will be two-sided, and a *P*-value ≤0.05 (two-sided) will be considered statistically significant for the tested differences. (Unless specifically stated otherwise)
- Descriptive analysis: For count data, describe with proportions. For measurement data,

- describe with mean, standard deviation, maximum, and minimum values. For non-normally distributed data, describe with median, 25th percentile, and 75th percentile.
- The comparison of general conditions between the two groups will be analyzed using appropriate methods based on the type of indicator. Inter-group comparisons of quantitative data will be performed using paired t-tests or Wilcoxon rank-sum tests. For categorical data, the chi-square test or exact probability method will be employed. For ordinal data, Wilcoxon rank-sum tests or CMH tests will be used.

12.2.1. Enrollment and study completion:

Summarize the number of enrollments and completions for each center and provide a list of dropouts. Different dataset sizes for each group, distribution of cases in each center, comparison of overall dropout rates, and a detailed list of reasons for termination. Describe the demographic characteristics of patients (age, height, weight, vital signs, etc.), medical history, and medication history. Compare age, height, and weight between the two groups to assess their comparability.

12.2.2. Compliance analysis:

- Medication compliance analysis: Compare whether patients in the two groups use the study drug on time and in the correct dosage, and whether they refrain from using prohibited drugs and foods according to the protocol.
- Concomitant medication analysis: Tally the number of patients in each group using concomitant medications and provide a detailed list.

12.2.3. Efficacy evaluation:

- Baseline: Describe the baseline characteristics of each efficacy indicator. Refer to general methods for inter-group comparisons.
- Primary efficacy endpoints:

Conduct both PP and FAS analyses concurrently. The primary time point for evaluating the proportion of patients with improved modified Rankin (mRS) scores ≤ 1 in terms of activities of daily living is at Day 90 (for the PP population) or at the time of premature discontinuation (for the FAS population). The primary indicator will be compared between the two groups using the CMH- χ^2 analysis method, controlling for center effects.

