The primary indicator will be assessed using a superiority test, testing the following hypothesis:

$$H_0: \pi_{Test\ group} - \pi_{Control\ group} \le 0$$

$$H_1: \pi_{Test\ group} - \pi_{Control\ group} > 0$$

$$\alpha = 0.025 (One - sided)$$

If the H_0 is rejected at the significance α level, or if the lower limit of the 95% CI for the difference in retention rates between the two groups is greater than 0, it can be considered that the treatment group is superior to the control group.

Other secondary indicators will be compared using the same statistical method as the primary indicator.

12.2.4. Safety evaluation:

Describe the number and proportion of subjects with normal values before treatment and abnormal values after treatment for both the treatment group and the control group separately. Describe adverse events using the number of cases, the number of subjects, and the incidence rate. Conduct inter-group significance tests will be conducted on the incidence rate. Additionally, provide a detailed description of the specific manifestations, severity, and the relationship with the drug for all adverse events observed in each group. Provide a cross-tabular description of the changes in laboratory indicators before and after the treatment. Compare vital sign indicators before and after the treatment.

13 Data Management

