6.2.4 Efficiency evaluation

Baseline efficiency: Describe the baseline of each curative index, and comparison between groups should be made in accordance with general condition. Modified Rankin (mRS) score is regarded as ranked data, and should be compared with Wilcoxon rank sum test. NIHSS score should be regarded as quantitative data and ranked data (4-7 points, 8-14 points and 15-22 points) for description and comparison; BI score as quantitative data and enumeration data (<85 points, ≥85 points) for description and comparison.

Primary efficiency indexes:

PP analysis and FAS analysis should be performed at the same time; evaluation on patients with modified Rankin (mRS) score≤1 should be mainly conducted ontaken at day 90 day (PP set) and the time for suspending and drop-out (FAS set). Primary indexes should be compared between the two groups with CMH-γ2 method for controlling central effect.

Superiority test is adopted for primary indexes, and the hypotheses under test are as follows:

$$H_0$$
: $\pi_{\text{treatment group}} - \pi_{\text{control group}} \le 0$

$$H_1: \pi_{\text{treatment group}} - \pi_{\text{control group}} > 0$$

$$\alpha = 0.025_{\text{(one-sided)}}$$

The treatment group is superior to control group, if H0 is rejected under α level, or lower limit of 95% Cl for difference of retention rate between the two groups is higher than 0. Take sensitivity analysis on primary efficiency indexes with modified Rankin (mRS) score≤2 points as the limit.

Other secondary indexes can be statistically analyzed in accordance with methods for primary indexes.

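### The confidence-interval limb of the primary success rule names retention rates instead of mRS ≤1 at 90 days, and its interval method is not stated

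*Combined protocol and SAP*

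**What the plan says.** The primary endpoint is given in protocol section 7.1.1 as "Improvement in self-care ability (proportion of patients with mRS score ≤1) after 90 days of treatment"; SAP section 5.1 agrees.

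On the test, protocol section 12.2.3 states: "The primary indicator will be compared between the two groups using the CMH" chi-square "analysis method, controlling for center effects". It continues: "The primary indicator will be assessed using a superiority test, testing the following hypothesis". The hypotheses concern the difference between the two groups' proportions, at one-sided α of 0.025.

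The sentence after the hypotheses gives two ways to conclude superiority, joined by *or*: H0 is rejected, or the lower 95% limit is above 0 for the "difference in retention rates between the two groups". SAP section 6.2.4 has the same structure and the same term: "difference of retention rate between the two groups is higher than 0".

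SAP Table 7.3.2.1, the shell for the primary result, has rows for mRS ≤1 and >1 at 90 days, then a statistic, P value, rate difference and 95% CI. Its note says that the CMH test handles centre. It does not say how the interval is calculated.

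**The concern.** This sentence decides whether the trial is positive. Its second limb is enough on its own for a positive conclusion, yet it refers to a quantity that neither document defines or lists as an endpoint. In ordinary trial usage, retention means patients staying in the study. Followed literally, the clause could therefore be met by better completion in the Tongxinluo arm, whatever happened to function.

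Once the term is read as mRS ≤1, a smaller gap remains. The first limb is adjusted for centre, while the second has no stated estimator, variance or stratification. With 50 planned centres, and with centre absent from the listed minimisation factors, a test that adjusts for centre and an interval that ignores it can disagree. Disagreement falls in borderline results, which is where a pre-specified rule has to settle the answer. Both documents also send the other secondary indicators to the primary method, so the gap carries over to them.

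**Working it through.** **Inputs.** Protocol 4.2 and SAP 4.4 give 40% versus 47% with mRS ≤1, two-sided α 0.05, power 80%, 787 per group, a 20% dropout allowance, 1,968 in total and 50 centres. Protocol 11.4.1 and SAP 4.2 list the minimisation factors as thrombolysis and NIHSS band; centre is not among them. The documents do not give the centre sizes, the between-centre variation or the interval method. The first two are assumed below, and the interval method is varied.

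**1. The plan's own figure.** With the pooled-variance formula:

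n per group = [1.960·√(2 × 0.435 × 0.565) + 0.8416·√(0.40 × 0.60 + 0.47 × 0.53)]² / 0.07² = (1.3741 + 0.5886)² / 0.0049 = 786.2, rounded up to 787.

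Dropout: 787 / 0.8 = 983.75, so 984 per group and 1,968 in total. Both figures reproduce. One-sided 0.025 also gives 787, so the sample size does not depend on the faulty clause.

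**2. Which quantity is meant.**

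| Place | Quantity |
|---|---|
| Protocol 7.1.1, SAP 5.1 (endpoint) | mRS ≤1 at 90 days |
| Protocol 12.2.3, SAP 6.2.4 (CMH test) | primary indicator, mRS ≤1 |
| Protocol 12.2.3, SAP 6.2.4 (hypotheses) | primary indicator |
| Protocol 12.2.3, SAP 6.2.4 (interval limb) | retention rate |
| SAP Table 7.3.2.1 | mRS ≤1, with rate difference and 95% CI |
| SAP Table 7.1.1.1 | drop-out and completion by group, no interval |

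Only the interval limb departs from mRS ≤1, and the only primary-result interval in the shells is for mRS ≤1.

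**3. Nominal level of the two limbs.** A one-sided 0.025 test rejects when Z > 1.96. The lower limit of a two-sided 95% interval is above 0 when estimate/SE > 1.96. The critical value is the same, so any disagreement comes from a different estimate or standard error.

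**4. Effect of the interval method.** For centre k with m patients, n₁ and n₀ per arm, x₁ and x₀ responders and t = x₁ + x₀:

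- CMH: Z = Σ(x₁ − n₁t/m) / √Σ[n₁n₀t(m − t) / (m²(m − 1))]
- Crude Wald: (P₁ − P₀) / √[P₁(1 − P₁)/N₁ + P₀(1 − P₀)/N₀], pooled over centres
- Stratified: Mantel-Haenszel risk difference with weights n₁n₀/m and Sato variance

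Null simulation: 40,000 trials per setting, 50 unequal centres, 40% in both arms, allocation not balanced by centre. One-sided rejection rates and disagreement with CMH, in %:

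| n per group | Centre SD (logit) | CMH alone | CMH or crude | Disagree | CMH or stratified | Disagree |
|---|---|---|---|---|---|---|
| 787 | 0 | 2.48 | 2.86 | 0.79 | 2.50 | 0.04 |
| 787 | 0.3 | 2.57 | 3.04 | 0.99 | 2.58 | 0.02 |
| 787 | 0.6 | 2.51 | 3.27 | 1.42 | 2.54 | 0.05 |
| 787 | 1.0 | 2.54 | 3.48 | 1.98 | 2.56 | 0.04 |
| 984 | 0 | 2.40 | 2.78 | 0.75 | 2.44 | 0.04 |
| 984 | 0.3 | 2.33 | 2.83 | 0.98 | 2.34 | 0.02 |
| 984 | 0.6 | 2.42 | 3.20 | 1.51 | 2.45 | 0.04 |
| 984 | 1.0 | 2.50 | 3.44 | 1.91 | 2.54 | 0.05 |

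The simulation error on a 2.5% rate is √(0.025 × 0.975 / 40,000), about 0.08 percentage points.

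A separate run at a 42% rate (20,000 trials per setting, centre SD 0.3/0.6/0.9) gave 2.47/2.54/2.65% for CMH alone, 2.93/3.29/3.62% with the crude interval and 2.50/2.58/2.68% with the stratified one. Across both runs, the crude-interval rule spans 2.78–3.62%.

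Under the planned 7-point effect (787 per group, SD 0.3), the crude interval and CMH disagreed in 5.1% of trials and the stratified interval and CMH in 0.17%.

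**The case against.** The strongest reply is that this is a slip of one noun with an obvious meaning. The hypotheses and the CMH test refer to the primary indicator, Table 7.3.2.1 places the 95% CI beside the mRS ≤1 rate difference, and the drop-out table has no interval. Stating a criterion as a rejected null or a lower limit above 0 is the usual way to give one rule in test and interval form. The P value and interval share a table whose note refers to centre adjustment, so a centre-adjusted interval is the natural reading. On that reading the error rate is that of CMH alone to within 0.04 percentage points.

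Most of this stands. It establishes what was meant, and it makes the error inflation conditional. It does not remove the defect. The wrong term passed from the protocol into the SAP, inside a clause that alone suffices for success. The table note names a test and leaves the interval method open, so nothing in the text rules out a crude interval.

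A reader might infer that the whole success rule is written for retention. The documents do not support that: only the interval limb carries the term. A reader might also infer that the *or* always gives two chances to win, so that 0.025 is not kept. That fails when the interval uses the CMH strata.

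**Conclusion.** The interval limb is wrong as written in both documents and should be corrected before unblinding. The intended quantity, the proportion with mRS ≤1 at 90 days, can be identified from the rest of the plan.

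The statistical consequence depends on a choice that the documents leave open. A crude Wald interval would put the either/or rule at about 2.8–3.6% one-sided error against the stated 2.5%. A centre-stratified interval would leave it at about 2.5%, with the two routes disagreeing in roughly 0.02–0.06% of null trials. These figures rest on 50 unequal centres, a 40–42% rate, logit-scale centre SD of 0 to 1.0 and allocation not balanced by centre; the centre sizes and SDs are assumptions.

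One further inference should be resisted. The general two-sided 0.05 rule and the one-sided 0.025 of the superiority test do not conflict, because for a benefit of treatment they share the critical value 1.96. The planned 787 per group and 1,968 in total stand.

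**What to change.** In protocol section 12.2.3 and SAP section 6.2.4:

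- Keep the centre-stratified CMH test of mRS ≤1 at 90 days, in the FAS at one-sided 0.025, as the single decision rule. SAP section 6.1.1 already makes the FAS the main efficacy population.
- Replace the retention term with the proportion with mRS ≤1 at 90 days, and delete the *or* route.
- Report a two-sided 95% CI for the Mantel-Haenszel risk difference, stratified by centre as in the CMH test and with a named variance (for example Sato), as the matching estimate. Add the method to the note under SAP Table 7.3.2.1.

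This keeps the test that the plan already names as primary. It costs about one sentence in each document plus a table note, with no new data and no change to sample size or nominal alpha.

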9.1 Efficacy determination criteria

9.1.1 Primary efficacy assessment

• The proportion of patients with improvement in activities of daily living 90 days after treatment (mRS score ≤1): mRS ≤1 indicates complete or substantial recovery of activities of daily living, representing a favorable prognosis. Comparison of the proportion of patients with favorable prognosis in the treatment group and the control group 90 days after randomization;

9.1.2 Secondary efficacy assessment:

- Improvement in neurological deficit, i.e., the proportion of patients with NIHSS ≤1 or NIHSS improved by 4 points or more: NIHSS score ≤1 or reduction of ≥4 points is considered effective; compare the proportion of effective and ineffective patients and continuous changes of NIHSS in the treatment group and the control group after 90 days of randomized treatment;
- Proportion of patients with BI index ≥85: BI score ≥85 indicates the ability to live
 independently. Compare the proportion of patients able to live independently between
 the treatment group and the control group 90 days of randomized treatment, as well as
 continuous changes in BI scores between the two groups;
- Disability rate, defined as the proportion of patients with an mRS score ≥3: An mRS score ≥3 indicates the inability to live independently. Compare the percentage of disabled patients between the treatment group and the control group 90 days of

randomized treatment:

- Continuous changes in mRS scores: Compare the changes in mRS scores between the treatment group and the control group at different visit points, including baseline, 7 d, discharge, and 90 d;
- Incidence of ischemic cerebrovascular events during the follow-up period: The
 proportion of ischemic stroke or TIA within 90 days of randomized treatment, or
 newly occurring ischemic lesions detected on MRI at the last visit, will be assessed as
 a group or separately;
- Incidence of combined vascular events during the follow-up period: The cumulative
 incidence of newly occurring combined vascular events within 90 days of randomized
 treatment will be assessed as a group or separately;

Definition of combined vascular events: Consist of any type of stroke (ischemic stroke, hemorrhagic stroke), TIA, myocardial infarction, and vascular death.

Vascular death: Hemorrhagic death of any organ or fatal pulmonary embolism.

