5.2 Secondary effect index

1. Improvement of neurological deficits (ratio of NIHSS≤1 or improve 4 score or more);

Improvement of neurological deficits (ratio of NIHSS≤1 or improve 4 score or more): It is effective for NIHSS≤1 or reducing 4 points or more; compare the ratio of efficacy and inefficacy and the continuous change of NIHSS between treatment group and control group 90 days after random treatment;

2. Improvement of daily life ability (ratio of BI index ≥85);

Ratio of patients with BI index≥85: BI score≥85 indicates the patient with ability of independent living; compare the ratio of patient with ability of independent living and continuous change of BI between treatment group and control group at 90 days after random treatment;

3. Disability rate (ratio of mRS score \geq 3)

mRS≥3 indicates the patient without self-care ability; compare the disability rate between treatment group and control group at 90 days after random treatment;

4. Continuous change of mRS score

Compare change of mRS score at baseline, 7d, discharge day and 90d between treatment group and control group;

5. Incidence of ischemic cerebrovascular diseases during follow-up period;

Ratio of ischemic stroke or TIA within 90 days after random treatment, or ratio of new ischemic focus detected by MRI during the last visit, and take this kind of patients as a group for evaluation or respective evaluation:

6. Incidence of combined vascular events during follow-up period;

Accumulated ratio of patients having newly combined vascular events within 90 days after random treatment;

Definition of combined vascular events: Include any type of stroke (ischemic stroke and hemorrhagic stroke), TIA, myocardial infarction and vascular death.

Vascular death: Hemorrhagic death or fatal pulmonary embolism of any organ.

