6.2 Statistical method

6.2.1 General principle

SAS9.4 software is adopted for statistical analysis. All data are performed with two-sided test, and P value less than or equal to 0.05 (two-sided test) is considered with statistical difference. (Unless the special instruction)

Quantitative indexes are described with case number, mean, standard deviation, median, P25 (Q1), P75(Q3), minimum value (Min) and maximum value (Max).

Classification indexes are described with case number and percentage.

Comparison of general situation should be analyzed with appropriate method based on the type of indexes. Quantitative data should be analyzed with paired t test or Wilcoxon rank sum test; classification data with chi-square test or precise probability method, and ranked data with Wilcoxon rank-sum test or CMH test.

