6.2.6 Exploratory analysis

Take predicted subgroup analysis on primary indexes;

7. Results of statistical analysis

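### Secondary endpoints are each read at P ≤ 0.05 with no gate on the primary, no test order, no alpha adjustment and no supportive label

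*Combined protocol and SAP*

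**What the plan says.** **Primary.** Protocol 12.2.3 and SAP 6.2.4 compare the proportion with mRS ≤1 between arms by a CMH test controlling for center. They add a superiority hypothesis at one-sided 0.025. SAP 6.1.1 and 6.1.2 make the FAS the main efficacy population and the per-protocol set (PPS) the secondary one.

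**Secondaries, method.** The protocol says "Other secondary indicators will be compared using the same statistical method as the primary indicator". The SAP is more permissive: "Other secondary indexes can be statistically analyzed in accordance with methods for primary indexes".

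**Significance rule.** Protocol 12.2 says "All statistical tests will be two-sided" and sets the threshold at 0.05. SAP 6.2.1 agrees: "P value less than or equal to 0.05 (two-sided test) is considered with statistical difference".

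**Secondaries, list.** Protocol 7.1.2 and SAP 5.2 list six: NIHSS response, Barthel Index (BI) ≥85, disability (mRS ≥3), continuous mRS change, ischemic cerebrovascular disease and combined vascular events. The synopsis lists five. It omits disability and gives mRS as an ordinal shift at 90 days.

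**More than one test per endpoint.** For mRS, SAP 5.2 says "Compare change of mRS score at baseline, 7d, discharge day and 90d between treatment group and control group". NIHSS and BI are each compared as a responder rate and as a score change. Protocol 9.1.2 allows both event endpoints to be assessed jointly or by component.

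**Exploratory label.** SAP 6.2.6 reads "Take predicted subgroup analysis on primary indexes". Its section 7.5 shells cover subgroups of the primary; no secondary endpoint appears there.

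**The concern.** Several secondaries are read at the same threshold as the primary, and nothing states what a significant one may be used for. If the primary missed, the plan as written would not prevent a result on NIHSS, BI, disability, mRS at one visit or a single vascular component from being reported as a positive finding at nominal alpha. If the primary succeeded, the secondary findings reported with it would still lack protection at the stated level as a set. A reader of the trial report could not tell from the plan which secondary results were meant as confirmatory.

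**Working it through.** **1. The plan's own figures.** No family-wise rate is stated for the secondaries. The stated alpha can be checked against the sample size (Protocol 4.2, SAP 4.4: 40% versus 47%, two-sided 0.05, power 80%). The mean proportion is 0.435.

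n = [1.960 × √(2 × 0.435 × 0.565) + 0.842 × √(0.40 × 0.60 + 0.47 × 0.53)]² / 0.07² = 786.2, so 787 per arm as stated.

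787 / 0.8 = 983.75, so 984 per arm and 1,968 in total, as stated. The cut-off is 1.960 for two-sided 0.05 and for one-sided 0.025. Each test therefore carries 0.025 in the favourable direction under either rule.

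**2. How many tests.**
- Six endpoints, one test each (Protocol 7.1.2, SAP 5.2).
- Post-baseline between-arm FAS tests in SAP Tables 7.3.3 to 7.3.8, leaving out the repeated ischemic stroke table: NIHSS 3 (response, Day-90 score, change); BI 3; disability 1; mRS 6 (score and change at three visits); ischemic events 4 (stroke, TIA, new MRI focus, composite); vascular events 3 (myocardial infarction, vascular death, composite). 3 + 3 + 1 + 6 + 4 + 3 = 20.
- The BI score shell refers to a blood-pressure table, so two of the 20 are inferred from the NIHSS layout.

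**3. Chance of at least one false favourable result.** All secondary nulls are taken as true, with m standard normal statistics sharing a common correlation ρ:

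rate = 1 − ∫ [Φ((1.96 − √ρ·z)/√(1 − ρ))]^m φ(z) dz

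At ρ = 0 this is 1 − 0.975^m: 1 − 0.975^6 = 0.141 and 1 − 0.975^20 = 0.397.

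| ρ (assumed) | six tests | twenty tests |
|---|---|---|
| 0 | 14.1% | 39.7% |
| 0.3 | 12.2% | 28.0% |
| 0.5 | 10.4% | 21.0% |
| 0.7 | 8.2% | 14.5% |
| 0.8 | 6.9% | 11.2% |
| 0.9 | 5.4% | 7.8% |

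The single-test benchmark is 2.5%. At ρ = 0.5 six tests give 10.4 / 2.5 = 4.2 times that; at ρ = 0.9, 5.4 / 2.5 = 2.2 times. Counting significance in either direction at two-sided 0.05, six tests give 26.5% at ρ = 0 and 20.7% at ρ = 0.5, against 5%. With the synopsis list of five, the favourable-direction rate at ρ = 0 is 1 − 0.975^5 = 11.9%, and about 9% at ρ = 0.5.

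**4. After a change.** A gate on the primary followed by a fixed sequence, each step at one-sided 0.025, holds the whole confirmatory set at 2.5% one-sided. Bonferroni over six (0.025 / 6 = 0.0042 one-sided) would hold the six secondaries at 2.5%.

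**The case against.** **The superiority rule may not carry over.** A reader might infer that every secondary inherits the primary's superiority declaration, since the sentence on secondaries follows that rule directly. The text does not establish this. Both documents confine the superiority hypothesis to the primary, and the SAP says only that its methods can be used. The alternative hypothesis, treatment minus control above zero, points the wrong way for disability and vascular events and does not fit a score change. The primary shell has rows for a rate difference and 95% CI; the binary secondary shells have only a statistic and P value. This objection stands. It leaves the per-test alpha unchanged, because the general P ≤ 0.05 rule gives the same figure.

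**No formal claim is promised.** Also true: neither document says a secondary will support a claim if the primary fails. Neither rules it out, and no label limits the secondaries to a supportive role.

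**The error rates are soft.** They need a correlation the documents do not give, and they assume no true effect on any secondary. The 20 tests overlap heavily (score and change of the same scale, components inside composites), so zero correlation is unrealistic for them and 40% is an outer bound. This stands and is why ranges are given.

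**The PPS should not be counted as doubling the claims.** Accepted: the SAP ranks it second.

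**The mRS does have a stated visit.** The synopsis fixes the mRS distribution at 90 days. Protocol 7.1.2 and SAP 5.2 do not, so the passages conflict.

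**Conclusion.** The point holds in a limited form. Every secondary comparison is read at nominal two-sided 0.05, with no condition on the primary, no order, no adjustment and no supportive label. The favourable false-positive rate is about 5% to 14% for six endpoints and about 8% to 40% for the tabulated FAS tests, for common correlations from 0.9 to 0. At an assumed 0.5 the rates are about 10% and 21%. Those two values should not be quoted as the trial's error rate: they describe two different families under one assumed correlation. The qualitative conclusion does not depend on it, since six tests at 0.9 still give about twice the single-test level.

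Nor should a reader infer that the primary result is compromised. There is one named primary endpoint and one main population, and its type I error is untouched. The gap lies in what may be concluded from the secondaries, and wording can close it.

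**What to change.** Amend Protocol 12.2.3 and SAP 6.2.4 before the first unblinding:

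1. Reconcile the five secondaries in the synopsis with the six in Protocol 7.1.2 and SAP 5.2, including whether the mRS secondary is the Day-90 shift. Name one Day-90 or within-90-day FAS contrast per endpoint and state the direction of benefit.
2. Choose one of two rules. Either allow a confirmatory secondary conclusion only if the primary FAS test rejects at one-sided 0.025, then test in an order the sponsor prespecifies, each at one-sided 0.025, stopping at the first non-significant result. Or state that all secondaries are supportive, with nominal P values and no superiority conclusion. The existing list order should not be adopted by default, as nothing shows that it reflects priority.
3. Under either rule, label as supportive mRS at 7 days and discharge, NIHSS and BI score changes, single event components and all PPS results. Report each with an estimate and 95% CI, adding those rows to the shells that lack them.

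The cost is wording in both documents and a few table rows. No patients, data or primary power are affected. The downside is that some secondary results may no longer support a formal claim.
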